TMS is a noninvasive method to cause depolarization or hyperpolarization in the neurons in the brain using electromagnetic induction to induce weak electric currents using a rapidly changing magnetic field. TMS is a novel intervention developed in the field of neurology that has been used in the treatment of patients suffering from migraine, stroke, Parkinson's disease, tinnitus and depression. In healthy subjects, high frequency rTMS over the left DLPFC has been shown to alter impulsive choice behavior (to decrease delay discounting) in healthy individuals and in smokers (12). On the other hand, a trial of TMS by one of the leaders in the field has shown it to be safe and well tolerated in recent suicide attempters suffering from depression with comorbid post-traumatic stress disorder and traumatic brain injury (13).

UAMS investigators have used repetitive transcranial magnetic stimulation (rTMS) to understand and treat phantom sound perception in subjects with tinnitus and to examine risky choices and impulsive behaviors using delay discounting in smokers. We propose to replicate a randomized controlled trial of rTMS over 3 days in a sample of well characterized acutely suicidal inpatients.

Our overall hypothesis is that 10 Hertz rTMS of the left dorsolateral prefrontal cortex (DLPFC) will correct impulsive choice behavior deficits found in acutely suicidal patients that in turn will translate into faster resolution of acute suicidal ideation. The current proposal will expand our understanding of the neurobiology of suicidal behavior by examining a potential neurocognitive mechanism of acute suicidality and test the value of rTMS as intervention for acute suicidal behavior. The current proposal will utilize behavioral assessments and rTMS in a randomized controlled trial in a group of adult patients hospitalized: a) following a recent suicide attempt with persistent suicidal ideation, or b) for severe suicidal ideation (n=20). To meet this goal we plan to recruit up to 28 individuals. Specifically, we propose:

The primary objective/endpoint of this study is safety. Adverse events will be collected throughout the duration of the trial. Any subject that meets the criteria for withdrawal (*Safety Assessments, page 14*) will be withdrawn from the study. The study will be stopped and all subjects withdrawn if two completed suicides by subjects receiving TMS occur during the active TMS treatment.

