Repetitive TMS (rTMS) will be delivered to the left PFC, defined as a location 6 cm (cm) anterior to the right hand motor thumb area. A research nurse will deliver the treatments. rTMS will be delivered with a figure-eight coil at 120% motor threshold, 10 Hertz (Hz), 5 s (s) train duration, 26 s intertrain interval for 50 min (6000 pulses) 3 times daily for 3 days (total 9 sessions, 54,000 stimuli). Similar parameters were previously used in a population of acutely suicidal veterans and military patients with even more severe comorbidity than our proposed sample because of comorbid posttraumatic stress disorder and traumatic brain injury without significant adverse effects (13). Variations will be allowed in the dosing schedule to accommodate the patient's inpatient schedule and staffing needs, with at least 1 hour between sessions. Treatments will be done on consecutive days, with the goal to deliver 9 sessions over three days. Adverse events will be assessed at each treatment session as well as daily. Prior to and then immediately after each rTMS session, subjects will complete visual analog scales (VAS) on a laptop computer located next to the rTMS chair. Patients will wear earplugs and will not be allowed to sleep. Counseling or other conversation during treatment will be discouraged.

Sham treatment

Parameters for sham rTMS are identical to those for active stimulation except that aluminum plate blocks the propagation of a magnetic field. The sound and physical sensation is the same as with the active coil while been biologically inactive.

Assessments

Trained and blinded study staff (raters) will administer assessments as described in Table 2. Additionally, menstrual cycle phase will be characterized for female subjects (i.e. date of last period, regularity of menstrual cycle).

PI: [name]

Table 2. Assessments administration schedule during the proposed study									
Task	Intake &	Pre rTMS	Post rTMS	Post	Before	3 & 6 month			
	Pre rTMS	Session 1	Session 3	rTMS	Discharge	follow-up			
	Session 1	(day 2 & 3)	(day 1 & 2)	Session 3					
	(day 1)			(day 3)					
Informed Consent Capacity	X								
Checklist									
Informed consent	X								
Demographic Data Form	X								
Columbia Suicide Severity Rating	X				X	X			
Scale (C- SSRS)									
Hamilton Rating Scale for	X			X	X	X			
Depression (HAM-D)									
Hamilton Anxiety Rating Scale	X			X	X	X			
(HAM-A)									
Beck Scale for Suicidal Ideation	X			X	X	X			
Beck Hopelessness Scale	X	X	X	X	X	X			

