Delay discounting task	X	X	X	X	X	X			
N back test	X	X	X	X	X	X			
Stroop Test	X	X	X	X	X	X			
Young Mania Rating Scale	X	X	X	X	X	X			
DKEFS Verbal Fluency Test	X	X	X	X	X	X			
Pressure pain threshold	X	X	X	X	X	X			
Sham validating measure				X					
Trail making A and B	X	X	X	X	X	X			
Visual Analog Scales**	X	X	X	X	X	X			
MINI International	X								
Neuropsychiatric Interview (MINI)									
Randomization	X								

^{**} This assessment will be collected 3 times per day pre and post rTMS.

Safety Assessments

Research staff will use the MedDRA System Organ Class (SOC) and preferred term (PT) to document adverse events, which will be assessed at each treatment, and at follow-up visits.

This protocol will not modify patient care and our visits will not interfere with regular clinical care, except in the case of imminent danger to the patient or others in which appropriate measures will be taken, like contacting the primary treatment team and placing the patient on 1:1 observation until evaluation by the primary team.

STUDY POPULATION

Participant recruitment will occur at the inpatient units at the Psychiatric Research Institute (PRI). Target sample size is 20, which will be randomized into active or sham groups (1:1). Considering 40% attrition rate we plan to recruit 28 participants.

Recruitment: Recruitment will be facilitated by the PI's role of PRI inpatient attending physician. The success of this proposal depends heavily on the ability to recruit patients very soon after hospitalization for

PI: [name]

suicide ideation or behavior.

All participants will be compensated \$40 for their participation in each of the 3 rTMS sessions of the active phase of the study and the 2 follow-up sessions. Participants can earn a total of \$200 for completing the entire study, including both follow up visits.

Inclusion Criteria

- a) Age 18-60 years, of all races and ethnicities;
- b) Admitted voluntarily to the adult psychiatric inpatient at PRI;
- c) Suffering from a current depressive episode as defined by the DSM-V
- d) Currently have diagnoses of major depressive disorder
- e) Reason for hospitalization should be a recent suicide attempt or suicidal ideation
- f) Current severe suicidal ideation defined by a score >7 in the Beck Scale for Suicidal Ideation
- g) Must pass the TMS safety checklist (TASS)
- h) Women of childbearing age must have a negative result on a pregnancy test
- i) Ability to read, write and speak English.

Exclusion Criteria

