- 11. Risk of vision changes. Temporary changes in visual fields may be noticed immediately after TMS. These visual abnormalities are not thought to be actual problems with the eyes, rather changes in brain functioning as a result of the TMS. Alterations in regional activation and neurotransmission may trigger things like blurred vision and/or eye floaters both of which normalize in time.
- 12. All the above risks are increased by performing rTMS stimulation at an intensity higher than what the FDA considers as a safe limit. For 10Hz frequency and 120% of the motor threshold, FDA considers the maximum safe train duration to be 4.2 seconds, instead of 5 seconds. However, our parameters are less aggressive than the one used by George et al. 2014 in a very similar population that were well tolerated by their study participants.

Risks Associated with Loss of Confidentiality

Likely: None.

Less Likely: None.

Rare: Confidential information about subjects may be accidentally disclosed. All data will be safe-guarded in accordance with HIPAA. The investigators use codes to keep subject information secure. Data encryption software is required at UAMS for computers with confidential information.

Risks Associated with Interviews and Ouestionnaires

Likely: Subjects may experience frustration and boredom completing the questionnaires that measure subjects' response to this experimental therapy. Subjects may decline to answer any questions that may make subjects uncomfortable, including questions that may be asked of subjects by the study physicians.

Risks Associated with Blood Draw

Likely: Subjects my experience discomfort associated with venipuncture. Some bleeding and bruising may occur.

PI: [name]

Rare: Infection at the site of blood collection and fainting are rare but possible risks associated with blood collection.

Protection Against Risks Associated with TMS

The following steps will be taken to minimize the risks associated with TMS. Additionally, subject exclusion criteria should eliminate subjects for whom risk is greater.

- 1. Subjects are fully informed of all risks during the informed consent process. . .

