- hearing gets worse during or after stimulation
- syncope during rTMS
- develop mania or hypomania during the TMS trial

The study will be stopped and all subjects withdrawn if two completed suicides by subjects receiving TMS occur during the active TMS treatment- as suggested by the FDA.

Adverse Events Reporting and Evaluation

All adverse events occurring during the course of the clinical study, whether device-related or otherwise, will be recorded on the Adverse Event Case Report Form. For all adverse events, the investigator will provide an assessment of the adverse event, its treatment and resolution, and its relationship to the investigational device. Special reporting procedures are required for certain adverse events.

PI: [name]

Identification of Adverse Events

An adverse event is defined as any new medical problem, or exacerbation of an existing problem, experienced by a subject while enrolled in the study, whether or not it is considered drug/device-related by the investigator.

Relationship of Adverse Events to the Investigational Device

The investigator will assess the relationship of the adverse event to the investigational device. The relationship will be assessed using the following categories:

- Definitely Related: A direct cause and effect relationship between the investigational drug or device/experimental treatment and the adverse event exists.
- Possibly Related: A direct cause and effect relationship between the investigational drug or device/experimental treatment and the adverse event has not been clearly demonstrated, but is likely or very likely.
- Unlikely Related: A direct cause and effect relationship between the investigational drug or device/experimental treatment and the adverse event is improbable, but not impossible.
- Unrelated: The adverse event is definitely not associated with the investigational drug or device/experimental treatment.

Unanticipated Adverse Device Effects

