Analyses of VAS data will be conducted using a similar MMRM approach. Each VAS item will be analyzed separately. For the suicide, mood and anxiety items, the model included as the dependent variable change scores from pre-session 1 (session prior to intervention) to each post-session (sessions 1-9) during the acute phase. Independent variables included treatment, session, treatment-by-session interaction, VAS score at pre-session 1, gender, age at baseline, and diagnosis. Painfulness questions collected only at each post-session will be analyzed using an MMRM approach with post-session scores as the dependent variable. Independent variables will remain the same.

Descriptive analyses will be performed to compare baseline data between treatment groups. Categorical variables will be evaluated using Fisher's exact test. Continuous variables will be analyzed with Wilcoxon's rank sum test.

Safety data will be summarized overall and by treatment groups. Fisher's exact test will be used to compare the number of subjects between groups who experienced any adverse events. Length of hospital stay will be compared using Wilcoxon Rank Sum test. Time to re-admission will be analyzed with log-rank test.

The Stroop Test, N-Back scores and pain pressure threshold will be added as covariates in final analysis. Other secondary efficacy outcomes (HRSD, MADRS, CAPS and SSI) for the extended safety phase will be analyzed with MMRM model. The model will include the change from baseline at each follow-up visit as the dependent variable. Independent variables include treatment, visit, treatment-by-visit interaction and base- line score.

We will use repeated measures ANOVA (with appropriate statistical corrections) to compare measures obtained at baseline to those collected 3 & 6 months after all experimental treatment ends. This analysis will address long-term effects of rTMS experimental treatment on suicidal ideation.

The integrity of the blind will be analyzed by tables and Fisher's exact test.

All statistical analyses will be performed in R version 2.14.0. Because this is an early phase study, no adjustments will be made for multiple comparisons, and a *P*-value of 0.05 will be considered to be statistically significant.

Power estimation

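### The between-arm adverse event test sets no time window, so events unrelated to stimulation can mask a treatment-day difference

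*Combined protocol and SAP*

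**What the plan says.** Safety is the primary objective in Background and Rationale, and Hypothesis 1 predicts that rTMS will be well tolerated. The only between-arm test of adverse events is in Data Analysis: Fisher's "exact test will be used to compare the number of subjects between groups who experienced any adverse events". The sentence gives no start or end date, no restriction by relatedness and no analysis population.

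What counts has to be taken from elsewhere:

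- Identification of Adverse Events covers a new or worsened medical problem "experienced by a subject while enrolled in the study, whether or not it is considered drug/device-related by the investigator".
- Background and Rationale: "Adverse events will be collected throughout the duration of the trial".
- Safety Assessments (within Study Design and Procedures): staff document "adverse events, which will be assessed at each treatment, and at follow-up visits". Table 2 puts those visits at 3 and 6 months.
- Active experimental treatment: "Adverse events will be assessed at each treatment session as well as daily".

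The order of events on entry also matters. Under Recruitment/Screening, consent comes first, then the baseline assessments, then a blood sample. Randomisation follows the baseline assessments. Of the blood draw, the risk section says: "Some bleeding and bruising may occur". No treatment-emergent definition appears anywhere.

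**The concern.** A single any-event indicator records at most one fact per subject. Once a subject has had a bruise at intake or an illness in month 5, a headache during stimulation cannot change that subject's status. If such background events are about equally common in both arms, they raise both proportions and shrink the difference between them.

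The loss runs in one direction. Equal background events do not create a false safety signal; they make a non-significant result more likely. That result agrees with the prediction that rTMS is well tolerated, so the dilution favours the hypothesis under test. In a trial of 20 subjects there is little power to spare.

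**Working it through.** **Plan's own figure.** There is none for this test. The Power estimation section addresses delay discounting and a tinnitus outcome, so nothing can be reproduced for adverse events.

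**Inputs from the documents.** Target sample 20, allocated 1:1, so 10 per arm; up to 28 recruited, so at most 14 per arm; significance level 0.05 with no multiplicity adjustment (two-sided assumed, as sidedness is not stated); 3 treatment days; last follow-up at 6 months (about 183 days).

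**Assumptions.** The documents give no any-event rate on treatment and no background rate. Let q be a subject's risk of an event on the treatment days and b the risk of an event outside them, equal in both arms and independent of q. Then

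P(any event) = 1 − (1 − q)(1 − b).

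For q = 70% active and 20% sham with b = 50%: active 1 − 0.30 × 0.50 = 85%; sham 1 − 0.80 × 0.50 = 60%. A 50-point difference becomes 25 points.

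**Exact power of the two-sided Fisher test, by full enumeration, q = 70% vs 20%:**

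| b | Any-event rates, active vs sham | Power, 10 per arm | Power, 14 per arm |
|---|---|---|---|
| 0% | 70% vs 20% | 43% | 65% |
| 10% | 73% vs 28% | 33% | 51% |
| 20% | 76% vs 36% | 25% | 42% |
| 30% | 79% vs 44% | 18% | 34% |
| 50% | 85% vs 60% | 10% | 20% |

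The 14-per-arm column assumes that all 28 recruits contribute, which the plan's own 40% attrition makes optimistic.

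**A smaller difference.** For q = 30% vs 10% with 10 per arm, power is 6% at b = 0, 5% at b = 10%, 3% at b = 30% and 2% at b = 50%. Here sample size is the main limit and a window recovers little.

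**A result that needs no assumed rates.** With 6 of 10 sham subjects counted as cases, even 10 of 10 active gives one-sided probability C(10,6)/C(20,16) = 210/4845 = 0.043 and two-sided p = 0.087. Once six sham subjects have had any event, no excess in the active arm can reach 0.05.

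**What b might be.** The treatment days are 3/183 = 1.6% of follow-up. With a constant background risk over 183/3 = 61 three-day periods, a three-day risk of 0.5% gives 1 − 0.995^61 = 26%; 1% gives 46%; 2% gives 71%. These are illustrations. Recorded rates could be lower, because after discharge events are sought only at two visits.

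**False positives.** With equal rates and 10 per arm, the exact type I error stayed at or below about 1.3% at the rates tried, so the cost is in power.

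**The case against.** A reader might infer that the plan fixes the count from enrolment to month 6, that the test is meant to judge only the three treatment days, and that background events will swamp them so that a real effect disappears. The documents do not support these readings.

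- The test sentence sets no period. The span to month 6 follows from joining the definition, the collection rule and the visit schedule. The defensible statement is that the window is unspecified.
- Nothing limits the safety question to three days. The section on effects on mood names worsening depression, mania and raised suicide risk, with follow-up to 6 months; Data Analysis refers to an extended safety phase; and a readmission would meet the hospitalisation criterion for a serious event. A whole-trial comparison is a legitimate question, and replacing it with a short window would remove late events from the only between-arm test.
- Swamping needs a background rate that is not given. At b = 10% the loss is moderate.
- Equal background rates are assumed. The trial's premise is that rTMS changes suicidal ideation, so follow-up events could differ by arm.
- The pre-session contribution is probably small. Table 2 puts intake and the first pre-session assessment in the same day-1 column, and venipuncture discomfort or bruising is the only pre-session event the documents name as likely.
- On-treatment tolerability is visible elsewhere. Post-session painfulness is compared between arms by MMRM, and adverse events are coded, graded for severity and relatedness, and summarised by group. A stimulation effect could be lost from this p-value without being lost from the report.
- No passage makes a non-significant Fisher test the criterion for Hypothesis 1.

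All of these points stand as limits on the claim. None supplies the missing window or separates treatment-day events from the rest in the one adverse event test.

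**Conclusion.** The concern holds in a limited form. The Fisher test has no window and, read with the definition and schedule, mixes pre-session, treatment-day and follow-up events in one count. Unrelated events can therefore mask a treatment-day difference and tilt the result towards reassurance. Under the assumed 70% vs 20% risks, even a 10% background costs about a quarter of the power with 10 per arm, and a 50% background costs more than three quarters. These figures rest on event rates that the documents do not give and on equal, independent background risk. For modest differences the test is close to powerless with or without a window, so the window is one weakness and the sample size is another.

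**What to change.** State the following in Data Analysis before the blind is broken, so that the window is not chosen with results in hand:

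1. **Treatment-period comparison.** In subjects who started at least one session (the population the plan already uses for its mITT analysis), compare between arms the number with an event that starts or worsens from the start of session 1 to a short, pre-specified time after the last session. Give the risk difference with an exact confidence interval beside the Fisher p-value, since at this sample size the interval says more.
2. **Longer comparison, kept separate.** Compare events from session 1 through month 6 between arms, with the number of subjects still observed, so that late mood, suicidality and readmission events stay in view.
3. **Baseline listing.** List events before session 1 separately and exclude them from both comparisons.

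The cost is a few sentences and one extra safety comparison. Onset date and time must be available for each event; the adverse event form is not in the documents, so whether it already records them is unknown. No new visits are needed, because events are already assessed at each session and daily.

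### Fisher's exact test for adverse events is valid but conservative at this trial's size (true false-positive rate at most 1.3% at 10 v 10, about 2% to 3.3% at other plausible splits); Boschloo's exact test would add sensitivity at almost no cost

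*Combined protocol and SAP*

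**What the plan says.** All references are to the combined protocol and SAP.

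- DATA ANALYSIS has one between-arm test of adverse events. "Safety data will be summarized overall and by treatment groups", and Fisher's "exact test will be used to compare the number of subjects between groups who experienced any adverse events". Length of stay, time to re-admission and the visual analog items have their own analyses, but those are not adverse event tests.
- The same section makes no multiplicity adjustment and says that a P "value of 0.05 will be considered to be statistically significant". It does not say whether the adverse event test is one- or two-sided.
- BACKGROUND AND RATIONALE states: "The primary objective/endpoint of this study is safety". DATA ANALYSIS, however, calls delay discounting the primary outcome.
- STUDY POPULATION sets a target of 20 subjects, randomized 1:1, and adds: "Considering 40% attrition rate we plan to recruit 28 participants". The Randomization section uses blocks of 6.
- The documents give no expected rate of any adverse event by arm, and no power for this comparison. The nearest figure is head and neck pain in about 10% of subjects (Potential Risks).

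**The concern.** Fisher's test treats the total number of subjects with an event as fixed. In small, equal arms few tables are possible for a given total, so the P value moves in large steps and the 5% is mostly unused. The design itself fixes the arm sizes, not that total, and exact tests exist that use this.

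What is at stake is sensitivity. Hypothesis 1 predicts that rTMS will be well tolerated, so failing to detect an excess of events favours the hypothesis. At 10 v 10, a split of 8 active against 3 sham subjects with an event gives a Fisher P of 0.070 and a Boschloo P of 0.041.

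**Working it through.** **Inputs.** Fisher's exact test, threshold 0.05, target 20 at 1:1 (10 v 10), up to 28 recruited (14 v 14), blocks of 6: all from the documents. Two-sided testing is assumed. Event rates are assumed, as the documents give none by arm.

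**Which splits can occur.** Neither 20 nor 28 is a multiple of 6. If permuted blocks hold three per arm, 20 subjects are three full blocks plus 2. The last two go to different arms with probability 3/5, so 10 v 10 occurs 60% of the time and 9 v 11 or 11 v 9 occurs 40%. For 28, four full blocks plus 4, the chance of 2 and 2 is C(3,2) × C(3,2) / C(6,4) = 9/15, so 14 v 14 again occurs 60% of the time, otherwise 13 v 15 or 15 v 13.

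**Size of Fisher's test at 10 v 10.** With a common event rate p, size is the sum over rejected tables (a, b) of C(10,a) C(10,b) p^(a+b) (1−p)^(20−a−b). It peaks at p = 0.5, where every term is C(10,a) C(10,b) / 2^20. The tables with excess events on active and Fisher P ≤ 0.05 are:

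- sham 0, active 5 or more: 1 × 638 = 638
- sham 1, active 7 or more: 10 × 176 = 1,760
- sham 2, active 8 or more: 45 × 56 = 2,520
- sham 3, active 9 or more: 120 × 11 = 1,320
- sham 4, active 10: 210 × 1 = 210
- sham 5, active 10: 252 × 1 = 252

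The sum is 6,700. Doubled for the other direction, 13,400 / 1,048,576 = 1.28%. At lower event rates the size is smaller: 1.19% at 0.3, 0.76% at 0.2, 0.11% at 0.1, and it keeps falling towards zero.

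**Size of Boschloo's test at 10 v 10.** Order the tables by two-sided Fisher P and take the largest region whose maximum size is at most 5%. The cutoff is a Fisher P of 0.0867. The added tables (active v sham) are 4 v 0 (210), 6 v 1 (2,100), 7 v 2 (5,400), 8 v 3 (5,400), 9 v 4 (2,100) and 10 v 6 (210), sum 15,420. At p = 0.5 the size is (13,400 + 2 × 15,420) / 1,048,576 = 44,240 / 1,048,576 = 4.22%, which is also its maximum. The region contains Fisher's by construction.

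**Other splits, maximum size of Fisher's test.** 12 v 12 2.28%; 14 v 14 2.14%; 9 v 11 2.77%; 13 v 15 2.95%; 13 v 14 3.26%. So 10 v 10 is the lowest of these. If the test were one-sided at 0.05, the maximum at 10 v 10 would be 2.11%. Boschloo's two-sided maximum is 4.16% at 14 v 14 and 4.23% at 9 v 11.

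**Power, Fisher to Boschloo, in percent.** The sum is the same with separate rates for the two arms. The unequal columns show the gain in points, active arm size first.

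| Assumed rates, active v sham | 10 v 10 | 14 v 14 | Gain, 9 v 11 | Gain, 11 v 9 |
|---|---|---|---|---|
| 30 v 10 | 5.7 to 14.3 | 13.7 to 23.5 | 0.5 | 0.1 |
| 40 v 10 | 15.2 to 29.1 | 31.5 to 42.9 | 1.7 | 0.4 |
| 40 v 5 | 23.8 to 42.7 | 48.1 to 63.2 | 0.7 | 0.2 |
| 80 v 30 | 42.6 to 62.2 | 64.6 to 75.5 | 11.3 | 13.8 |
| 80 v 40 | 25.3 to 42.5 | 44.3 to 54.4 | 6.9 | 11.0 |
| 90 v 50 | 29.5 to 47.1 | 53.6 to 63.2 | 1.5 | 4.0 |

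At 14 v 14 the gain is smaller where Fisher's power is already high: 74.2 to 80.7 for 60 v 10, and 88.7 to 92.7 for 70 v 10. For a difference of 20 v 10 at 10 per arm, even Boschloo's power is only about 5%.

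**The case against.** **Fisher's test is valid and standard.** This stands. It keeps the error at or below 0.05, and the plan states a significance threshold, not an attained size. A reader might infer that the test breaches its stated level; it does not.

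**Conditioning can be defended.** If treatment affects no patient, the event total is fixed and only the assignment is random, so a conditional test is natural. Someone who insists on 5% within each event total would not accept Boschloo's added tables, whose Fisher P values run from 0.057 to 0.087. This is a real choice of reference set. It does not change the fact that Boschloo holds 5% over the two-arm design and gives up no Fisher rejection.

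**1.3% is the least favourable case.** This stands. A reader might take 1.3% as the trial's error rate, but it belongs to exactly 10 v 10, two-sided. The block size makes unequal arms quite likely, no safety population is fixed at 10 per arm, and the gain at unequal splits can be close to zero.

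**Patient protection does not rest on this P value.** This stands too. A reader might infer that the choice of test leaves subjects unprotected, or that this is the designated primary safety comparison. The plan gives the test no such label. It also has summaries by arm, grading and attribution of events, withdrawal criteria, a study stopping rule and a monitoring board.

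**The comparison is weak either way.** This is true, and an estimated difference with a confidence interval would tell a reader more than either P value. That does not argue for keeping the less sensitive test.

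**Conclusion.** The concern holds as a point of efficiency. At this trial's size Fisher's test uses between about a quarter (1.28/5 = 26%) and two thirds (3.26/5 = 65%) of the nominal 5%. Boschloo's test recovers some of the rest without exceeding 5% and without losing a Fisher rejection. The gain is clear in equal arms and anywhere from nothing to about 14 points at splits such as 9 v 11.

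The sizes follow from the arm sizes and two-sided testing alone. The power figures rest on assumed event rates. Boschloo's test does not make the comparison adequate for moderate differences: at 10 per arm and 30% v 10%, about six trials in seven would still miss the excess (100 − 14.3 = 85.7%).

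**What to change.** In the safety paragraph of DATA ANALYSIS, before unblinding, replace Fisher's test for the adverse event comparison with Boschloo's unconditional exact test, two-sided at 5%. State that arm sizes are treated as fixed and that the test statistic is the two-sided Fisher P value, since that definition guarantees that no Fisher rejection is lost. Add that a non-significant result will not be interpreted as evidence of safety.

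The cost is a few words of SAP text and a short script, to be named alongside the R version that the plan already specifies. No extra subjects or data are needed. The change should be made before results by arm are seen, so that the choice of test cannot depend on them.

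### The 3- and 6-month analyses leave out the day 3 and discharge scores, so a patient who never returns adds nothing and the long-term arm effect can be modestly biased

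*Combined protocol and SAP*

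**What the plan says.** Data Analysis sets out two long-term analyses.

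- **MMRM.** "Other secondary efficacy outcomes (HRSD, MADRS, CAPS and SSI) for the extended safety phase will be analyzed with MMRM model". Its response is given as "The model will include the change from baseline at each follow-up visit as the dependent variable", and its terms as "Independent variables include treatment, visit, treatment-by-visit interaction and base- line score".
- **Repeated measures ANOVA.** It is used "to compare measures obtained at baseline to those collected 3 & 6 months after all experimental treatment ends". Its purpose is stated: "This analysis will address long-term effects of rTMS experimental treatment on suicidal ideation".

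The acute-phase models in the same section use acute visits only, so no model links the two phases.

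Table 2 uses the label follow-up only for months 3 and 6. Its row "Beck Scale for Suicidal Ideation X X X X" has marks at intake, after the last session on day 3, before discharge, and at months 3 and 6. HAM-D has the same marks. MADRS and CAPS appear nowhere in the table.

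Study Population says: "Considering 40% attrition rate we plan to recruit 28 participants". It does not say at what stage those patients are lost. The documents give no imputation, auxiliary variable or missing-data sensitivity analysis for the follow-up period.

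**The concern.** An MMRM allows for loss that depends on observed scores only when those scores are in the model. Here the last scores before a patient can be lost to follow-up are outside it. A patient with a day 3 and a discharge score but no later visit has no row in the long-term MMRM. In a conventional ANOVA, a patient who misses either follow-up visit is dropped as well.

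Hypothesis 3.1 expects active rTMS to lower suicidal ideation. If patients who are still suicidal on day 3 return less often, more sham than active patients go missing. The sham patients who do return then look too well, and the long-term effect is understated. If loss works differently in the two arms, the bias can go either way. What is at stake is how the long-term estimate can be read, since the ANOVA is offered as the answer on lasting effects on suicidal ideation.

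**Working it through.** **1. Where each score enters**

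| Score (Beck SSI, HAM-D) | Long-term MMRM | Repeated measures ANOVA |
|---|---|---|
| Baseline | covariate, and subtracted from the response | level |
| Day 3, after last session | absent | absent |
| Before discharge | absent | absent |
| Months 3 and 6 | response | levels |

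**2. The plan's attrition figure.** The target is 20 and the recruitment figure 28. This reproduces as 20 × 1.4 = 28. Dividing by the retained fraction would give 20/0.6 = 33.3, or 34, and 28 × 0.6 leaves 16.8. That is a separate matter. Here what counts is that the timing is not given. If all 40% were lost after day 3, 8 of 20 patients (about 11 of 28) would add no outcome to the long-term MMRM.

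**3. When bias arises.** In SD units, the bias in the month 3 arm effect is β × Δ.

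- β is the slope of the month 3 score on the day 3 score given arm and baseline. With correlation r between day 3 and month 3, and 0.4 between each and baseline, β = (r − 0.4²)/(1 − 0.4²). That is 0.34/0.84 = 0.405 at r = 0.5 and 0.54/0.84 = 0.643 at r = 0.7.
- Δ is the difference between the returning patients of the two arms in how far their day 3 scores lie from the values expected from arm and baseline. Δ is zero if loss does not depend on the day 3 score. It is also zero if there is no acute arm effect and loss works the same way in both arms.

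**4. Size, by large-sample simulation.** Only the 40% comes from the plan. Assumptions: all 40% is lost after day 3; loss is logistic in the day 3 score, with one odds ratio per SD in both arms; correlation with baseline is 0.4. The comparison model adds the day 3 score. All rows below use r = 0.7.

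| Day 3 effect | Month 3 effect | Odds ratio | Loss, sham / active | Follow-up-only estimate | With day 3 | Understated by |
|---|---|---|---|---|---|---|
| 0.8 | 0.5 | 3 | 48% / 32% | 0.42 | 0.50 | 0.08 (16%) |
| 0.5 | 0.5 | 3 | 45% / 35% | 0.45 | 0.50 | 0.05 (11%) |
| 0.5 | 0.8 | 3 | 45% / 35% | 0.75 | 0.80 | 0.05 (6-7%) |
| 0.5 | 0.8 | 5 | 47% / 33% | 0.72 | 0.80 | 0.08 (9-10%) |

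In the first row, 0.08/0.643 gives Δ of about 0.12 SD.

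Over the full grid (both effects 0.5-0.8 SD, r 0.5-0.7, odds ratio 2-5) the understatement runs from about 2% to 25%, or roughly 0.02 to 0.13 SD. With a day 3 effect of 0.23 SD, the size that Power Estimation gives for the discounting rate, it is about 0.01-0.04 SD.

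Other loss patterns, at r = 0.5 with a true long-term effect of zero and logistic slopes of 1 to 2 per SD:

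- One shared mechanism at 20% loss, acute effect 0.5-0.8 SD: 0.03-0.09 SD.
- Dependence on response in one arm only, at 40% loss: 0.16-0.22 SD.
- Opposite dependence in the two arms, at 40% loss: 0.43 SD.

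Including day 3 removed the bias, to within simulation error, in every large-sample scenario.

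**5. Against sampling error.** With 40% random loss and r = 0.7, the standard error of the month 3 effect is 0.583 SD from 10 per arm and 0.473 SD from 14 per arm. A bias of 0.08 SD is 0.08/0.583 = 0.14 to 0.08/0.473 = 0.17 standard errors. Nominal 95% coverage falls to about 94.7%, and to 94.2-94.5% in the largest shared-mechanism case (about 0.125 SD).

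**6. Precision under random loss.** At r = 0.7, adding day 3 changes the standard error from 0.473 to 0.430 (14 per arm) and from 0.583 to 0.541 (10 per arm). The variance reductions are 1 − (0.430/0.473)² = 17% and 1 − (0.541/0.583)² = 14%. At r = 0.5 the reduction is no more than about 4%.

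**The case against.** The strongest reply is that this is a 20-patient pilot with safety as its stated primary objective, that these outcomes are secondary, and that the bias is a small fraction of a standard error. All of that stands, and it limits the weight of the point.

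It is also true that the 40% may fall before treatment or during the acute phase, where no day 3 score would exist, and that participants are paid for both follow-up visits. Post-discharge loss could therefore be well below 40%.

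Further, day 3 is not the last score before loss: discharge is. If loss depends on the discharge score (assumed correlation 0.8 with day 3), a model with day 3 alone keeps a bias of 0.01-0.02 SD. Loss driven by deterioration after discharge is not addressed by either score. The ANOVA does contain baseline, and its corrections are unspecified, so complete-case handling is the usual form rather than a stated rule.

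A reader might infer more than the documents support: that the long-term effect will be biased, that the bias is at least 10% once the correlation is 0.7 and the odds ratio 3, or that 40% of patients are expected to miss follow-up. The first needs the conditions in step 3 of the working. The second fails in the third row of the table. The third reads a timing into the attrition figure that it does not carry.

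None of this makes the follow-up-only model preferable. The rule that MMRM subjects need a baseline and one post-baseline SSI score does not rescue it either: a patient with only acute scores meets the rule but still has no response at a follow-up visit.

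**Conclusion.** The point holds as a cheap improvement. On the text, the acute Beck SSI and HAM-D scores enter neither long-term analysis, and nothing else in the plan deals with missing follow-up. Bias follows only under the conditions in step 3. The trial's own Hypothesis 3.1 makes the acute arm effect plausible, but the other conditions are unknown.

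The percentage range rests on assumed correlations, effects and odds ratios, and on placing the whole 40% after day 3. The consequence is a cleaner interpretation of the long-term estimate. A changed test result is unlikely at this sample size, and a gain in precision can be expected only if acute and later scores are strongly correlated.

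**What to change.** In Data Analysis, replace the extended-phase model for Beck SSI and HAM-D, the listed scales that Table 2 schedules. Fit one MMRM per scale with change from baseline at day 3, month 3 and month 6 as response levels, and add the discharge score as a further level if the model converges. Keep treatment, visit, their interaction and baseline score as terms. Include every mITT subject with a baseline and at least one post-baseline score on that scale. Take the month 3 and month 6 arm differences from this model as the main long-term estimates. An analysis of returning patients only may stay as supportive.

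The scores are already scheduled, so no visit, patient or assessment is added. The cost is in the unstructured covariance matrix, which has k(k+1)/2 parameters for k levels: 3 for the present two visits, 6 with day 3 (three more), and 10 with discharge as well (seven more). With so few patients the larger matrix may not converge, which is why the discharge level is conditional.
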